7.5 Dose Adjustments During Cyclosporine Therapy and Renal Insufficiency

7.5.1 Patients who subsequently develop renal insufficiency during the 6 month course of CSA (serum creatinine >1.5 , but ≤ 2.5 mg/dl) will have the dose decreased by 50% (see Appendix 2). The dose will be returned to the same planned dose (2-3 mg/kg) after the serum creatinine has returned to normal (<1.5 mg/dl). If patients do not tolerate the resumption of CSA to the full dose (recurrent increase in the serum creatinine, high CSA levels), patients should be maintained on the dose level that was able to achieve a therapeutic CSA levels without renal toxicity. Patients with a serum creatinine greater than 2.5 mg/dl will have the CSA held, and restarted only when the serum creatinine is ≤ 2.5 mg/dl, with the change in dosing schedule the same as described above.

8.0 Clinical Response Criteria

8.1 Complete Remission

A patient will be deemed to be in remission if all of the following criteria have been met within 4 weeks from enrollment and maintained after the tapering of plasma exchange:

- platelet count $\geq 150,000$
- normalization of LDH
- a decreased or unchanged serum creatinine compared to the creatinine measurement obtained at the time of enrollment.
- clinical improvement in neurologic findings/deficits without the development of new neurologic findings/deficits by exam or radiographic studies.

8.2 Partial Response

8.2.1 Patients showing improvement (increase in platelet count and a decrease in the LDH, but not meeting the full criteria for complete remission) should continue concurrent CSA or prednisone and plasma exchange therapy for up to 4 weeks. If at that time patients still have not met the criteria for remission, patients will be considered to have been unable to achieve remission but will remain on this protocol for the purposes of data and clinical sample collection and for safety monitoring, but may be treated at the discretion of their treating physician.

8.3 Refractory Disease

8.3.1 Patients not showing signs of improvement (partial or complete response) or benefit with daily plasma exchange and CSA therapy after 1 week of continuous therapy should be considered to have refractory disease. These patients will remain on this protocol for the purposes of data and clinical sample collection and for safety monitoring, but may be treated at the discretion of their treating physician and will be considered to have failed therapy.

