14.0 Statistical Analysis

14.1 Statistical Considerations-Sample Size Determination

For the study of the primary endpoint (treatment success rate), the sample size required is calculated based on the data from our previous publications. In these previous studies that looked separately at CSA/PE in 10 patients and at corticosteroids/PE in another 10 patients, we saw promising results that led to our hypothesis that CSA/PE treatment for TTP patients results in greater treatment response. In those studies, the primary endpoint was the proportion of patients who had TTP exacerbation, which is a more stringent endpoint that does not include other types of treatment failures such as refractory patients and/or death within 30 days post-PE. In the previous published pilot studies, we showed that 6/10 corticosteroid-treated patients exacerbated versus 0/10 CSA-treated patients. Combined with experience with subsequently treated patients, we observed an overall treatment success rate of 80% and 83% in refractory vs. de novo TTP patients, respectively, treated with CSA+PE versus 33% in those treated with corticosteroids+PE.

In terms of our primary endpoint of treatment success rate, we have designed a phase III trial that compares the proportion of treatment successes in each arm. Specifically, this study design will have at least 80% power to determine a significant difference in the treatment success rates between the arms if the true rates are 50% vs. 80%, assuming a significance level of 0.05 and a two-sided test. This reflects a clinically meaningful difference, and the data from our previous studies and experience support it as a feasible difference to detect. We plan to enroll a total of 72 patients to this trial (36 to each arm) to test the null hypothesis that there is no difference in treatment success rate between these treatments.

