Additionally, we will evaluate several secondary clinical endpoints through this trial, including: 1) exacerbation rate within 30 days post-PE; 2) clinical response rate; 3) the number of PE procedures required to achieve a clinical response; 4) relapse rate; and 5) safety and tolerability of each of the adjuvant treatments to PE. Each of the rates will be calculated assuming that these endpoints are binomially distributed, and 95% confidence intervals generated. For the exacerbation rate endpoint, we will only include those patients who have achieved clinical response (i.e. excluding refractory patients) and compare these rates between the two arms. We will have at least 80% power to detect a difference if the true exacerbation rates are 55% vs. 90% for this subset analysis (not adjusting for multiple comparisons); however, this comparison is distinctly ancillary to our primary clinical interest of achieving treatment success in all patients treated versus only keeping responding patients from experiencing TTP exacerbation. We will also evaluate relapse as a time-to-event variable, where Kaplan-Meier methods will be used to assess time to relapse from last plasma exchange in responding patients. The number of exchange procedures required to achieve clinical response will be assessed between arms using Poisson regression. Safety and tolerability data will be summarized by type of adverse event with frequencies calculated and compared between arms. In addition to these planned quantitative analyses, we will also use graphical

analyses to assess patterns and differences in these factors between the treatment arms.

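### The one-week refractory (failed-therapy) rule in 8.3.1 names only the CSA arm, although the rest of the plan treats refractory status as applying to both arms

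*Combined protocol and SAP*

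**What the plan says.** - **8.3.1 (Refractory Disease)** applies to "Patients not showing signs of improvement (partial or complete response) or benefit with daily plasma exchange and CSA therapy after 1 week". These patients stay on study for data, samples and safety, may be treated as their physician sees fit, and "will be considered to have failed therapy". Prednisone is not mentioned here, and no other section sets a one-week rule for that arm.
- **8.2.1 (Partial Response)**, the paragraph before, covers "Patients showing improvement (increase in platelet count and a decrease in the LDH, but not meeting the full criteria for complete remission" and says that they "should continue concurrent CSA or prednisone and plasma exchange therapy for up to 4 weeks". Both adjuncts are named.
- **8.1 (Complete Remission)** has no arm restriction: remission requires that all "criteria have been met within 4 weeks from enrollment" and are maintained after exchange is tapered.
- **14.1 (Sample Size Determination)** contrasts the pilot studies' exacerbation endpoint with "other types of treatment failures such as refractory patients and/or death within 30 days post-PE". This implies that refractory patients are failures for the primary endpoint, treatment success rate, and no arm is specified.
- **14.2 (Analysis Plan)** restricts the secondary exacerbation analysis to clinical responders ("i.e. excluding refractory patients) and compare these rates between the two arms").

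**The concern.** The trial is open-label and multi-center, so whoever applies 8.3.1 knows the arm. The rule has two effects: it labels the patient as failed, and it frees the choice of treatment. Followed as written, both effects reach the CSA arm at one week and never reach the prednisone arm, where a slow responder keeps the full four weeks of 8.1.

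The label matters because treatment success, the primary endpoint in 14.1, is never formally defined. The failure wording in 8.3.1 and the examples in 14.1 are most of what a scorer has to work from. Two sites, one reading 8.3.1 literally and one reading it as covering both arms, could classify the same patient differently, and each could cite the protocol.

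**Working it through.** **Step 1. The plan's own figure.** Section 14.1 gives 50% vs 80% success, two-sided 0.05, at least 80% power, and 36 per arm. The unpooled normal approximation gives n = (1.960 + 0.842)² × (0.5×0.5 + 0.8×0.2) / 0.30² = 35.8, so 36 per arm. The stated size reproduces, and correcting 8.3.1 does not change it.

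**Step 2. Is the arm restriction deliberate?**

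| Section | Subject | Arm named |
|---|---|---|
| 8.1 | Remission within 4 weeks | None (all patients) |
| 8.2.1 | Partial response, continue up to 4 weeks | CSA or prednisone |
| 8.3.1 | Refractory after 1 week, failed therapy | CSA only |
| 14.1 | Refractory patients as failures | None |
| 14.2 | Refractory patients excluded, arms compared | Both |

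Only 8.3.1 is restricted, and the plan gives no reason for a restriction. The comparison in 14.2 presupposes that refractory patients can occur in either arm. An omission is the likeliest explanation.

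**Step 3. Who would be scored differently under the literal text?** A patient who never remits misses the four-week window of 8.1 in either arm, so nothing changes for that patient. The difference is confined to a CSA patient who meets three conditions:

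1. no improvement or benefit after one week;
2. remission by week 4;
3. no failure up to 30 days after the last exchange.

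The same prednisone patient could count as a success. The exacerbation analysis set in 14.2, being defined by clinical response, could change only for these same patients.

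**Step 4. How common is that patient?** The documents do not say. What they do give points to few or none:

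- Improvement under 8.2.1 is a low bar: a platelet rise with an LDH fall.
- In the upfront CSA cohort (3.2), 11 of 12 remitted, after a median of 5 daily exchanges.
- Steroid-treated remitters took 4 to 10 days (2.6, Table 1).
- The slower CSA course in 3.1 (median 11 exchanges, range 5 to 45) comes from patients treated for exacerbation or refractory disease. It is not evidence about initial therapy.

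**Step 5. Sensitivity, on assumed inputs only.** Method: exact binomial enumeration, 36 per arm, uncorrected Mantel-Haenszel chi-square, two-sided 0.05, unstratified because the recurrent/de novo split is not given. The affected share of CSA patients (1% or 2%) and the common null rate of 65% (midpoint of 50% and 80%) are assumptions.

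| CSA patients affected | Power, 50% vs 80% less the share | Chance of significance favouring prednisone, both arms truly 65% |
|---|---|---|
| 0% | 77.2% | 2.4% |
| 1% | 73.8% | 2.9% |
| 2% | 70.1% | 3.5% |

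The 77.2% in the first row is below 80% because the test differs from the formula in Step 1. That gap has nothing to do with 8.3.1.

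The smallest possible non-zero change is one patient, 1/36 = 2.8% of the arm. With 27/36 vs 18/36 the statistic is 4.733 (p = 0.030). With 26/36 vs 18/36 it is 3.688 (p = 0.055). At an assumed 1% share, 0.99³⁶ = 70% of trials would contain no affected patient at all.

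**The case against.** The strongest reply is that the plan already answers the question. Section 8.0 sets response criteria for patients generally, the adjacent paragraph names both drugs, and both statistical sections use refractory status without favouring an arm. Section 8.5.2 (relapse) also mentions only CSA, which suggests wording carried over from the earlier CSA studies. Bias arises only if someone applies the least plausible reading, and nothing in the documents shows that anyone did. This stands as an argument about likelihood. It does not make 8.3.1 correct as written, and 8.5.2 does not help, since it concerns recurrence beyond 30 days and does not decide the primary endpoint.

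A reader might be tempted to go further in three ways that the documents do not support:

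- **That the CSA non-improver is irrevocably a failure.** Section 8.1 deems anyone meeting its criteria within four weeks to be in remission and makes no exception for patients earlier called refractory. For a late CSA remitter, 8.1 and 8.3.1 give competing labels. Which one governs is unknown, because treatment success is undefined.
- **That the pilot rate shows the rule was meant for both arms.** The earlier success rate in 14.1 ("versus 33% in those treated with corticosteroids+PE") matches (10 − 6)/12 = 4/12 from 2.6. But 14.1 says that later patients were included, so the denominator is not known. Even a true 4/12 would show only that non-remitters counted as failures; it says nothing about a one-week rule.
- **That the trial loses a known amount of power.** The figures in Step 5 follow from an assumed share with no basis in the documents. The pair of tables was chosen to straddle 0.05, and one changed outcome for any reason would do the same.

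**Conclusion.** The inconsistency stands and should be corrected. As written, 8.3.1 is an arm-specific failure and rescue rule that bears on the primary comparison of an open-label trial, and the rest of the plan contradicts it.

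Where the 8.3.1 label decides the scoring, it can only lower the CSA success rate, so the bias runs against CSA. If every site and analyst reads the rule as covering both arms, there is no bias. The size cannot be derived from the documents and is probably small, possibly zero.

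The conclusion rests on two inferences: that the missing words are an omission, and that refractory disease counts against treatment success (from 14.1 and the failure wording in 8.3.1). The case for acting is that a failure rule should read the same in both arms and costs almost nothing to correct. It does not rest on a large expected effect.

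**What to change.** In 8.3.1, replace the reference to plasma exchange with CSA by *daily plasma exchange and the assigned adjunct (CSA or prednisone)*. When treatment failures are classified for analysis, apply that full criterion, including its allowance for clinical benefit, identically in both arms.

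The cost is a few words. No added data should be needed: platelets and LDH are measured daily during exchange (9.2.1), and patients in both arms are hospitalized and monitored for response (10.0.1).

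Section 14.2 says that accrual has already passed the internal pilot, so the team may wish to confirm that week-1 classifications made so far were the same in both arms. This is optional, since nothing in the documents suggests that they differed. If it is done, patients should not be re-scored from platelets and LDH alone, because the criterion is wider than that.

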8.4 Exacerbation/Relapse Determination

8.4.1 Criteria to determine recurrences of disease and the need for re-initiation of therapy with plasma exchange will be the same as those to diagnose TTP (section 5.2.1). Patients requiring the reinstitution of plasma-based therapy (plasma exchange or infusion) within the first 30 days after discontinuing PE will be considered to have an “exacerbation” of their TTP.

8.4.2 Patients with a recurrence of TTP at a time point greater than 30 days from the end of plasma exchange therapy will be considered to have a "relapse" for the purposes of this study.

8.5 Treatment after Recurrences of TTP

8.5.1 Patients suffering exacerbations of TTP as described in the protocol (Section 6.4) after treatment on the corticosteroid arm of this study may then be treated with CSA concurrent with the resumption of plasma exchange at the same dose and schedule as described in the CSA arm of this randomized trial, assuming that they still meet enrollment criteria (including the serum creatinine). Patients will also discontinue the corticosteroids on the same day that CSA is initiated. Patients treated with CSA and PE for exacerbations of TTP will then be prospectively followed as described below (Section 9.3 – 9.5), but will be analyzed independently from the patients treated with CSA and PE as the upfront therapy.

8.5.2 Patients suffering a relapse (recurrence greater than 30 days after the last exchange procedure) whether during CSA or after completing 6 months of CSA will continue to be followed on this study for the purposes of gathering follow-up data, but may be treated at the discretion of the treating physician.

9.0 Clinical Studies

9.1 Laboratory Studies at Enrollment

9.1.1 The initial laboratory tests will be obtained at the time of enrollment on this study. Laboratory tests will include (see Appendix 1):

- CBC (complete blood count), platelet count and evaluation of the peripheral smear
- chemistry panel (Na, K, Cl, CO₂, Cr, BUN, Ca, and glucose), total and direct bilirubin
- LDH (lactate dehydrogenase), haptoglobin
- PT /PTT /Fibrinogen
- Direct antiglobulin test (DAT)
- liver function tests (AST, ALT, GGT, Alkaline Phosphatase)

9.1.2 We will collect at least 100 cc plasma and 10 cc/2 teaspoons of whole blood prior to beginning of the plasma exchange for following laboratory investigations:

- ADAMTS13 activity
- ADAMTS13 inhibitor assay

- ADAMTS13 antigen level

9.2 Laboratory Studies During Plasma Exchange

- 9.2.1 During plasma exchange therapy, the following labs will be obtained daily (see Appendix 1):
 - CBC with a differential and platelet count
 - chemistry panel (Na, K, Cl, CO₂, Cr, BUN, Ca, and glucose) with LDH

9.3 Laboratory Studies During Plasma Exchange-Cyclosporine Monitoring

- 9.3.1 For patients randomized to the CSA arm of the study, CSA concentrations should be obtained on the 3rd day of PE, and then weekly thereafter as long as they remain in the hospital concurrent CSA and PE (see Appendix 1).
- 9.3.2 Samples for CSA levels should be obtained in the morning, prior to the first dose of CSA in order to obtain trough levels of CSA (section 7.4.2).

9.4 Outpatient/Remission Follow-up and Correlative Laboratory Studies

- 9.4.1 After discharge from the hospital, patients will be seen weekly in the outpatient clinic for the first month. Patients will then be seen monthly for the next 6 months, regardless of which arm of the study they were randomized to (see Appendix 1).

- 9.4.2 The following laboratory studies will be obtained at each follow-up visit:

- CBC with a platelet count
- chemistry panel (Na, K, Cl, CO₂, Cr, BUN, and glucose), total and direct bilirubin
- LDH
- cyclosporine concentration (patient should be told not take their CSA dose until after the blood has been drawn to ensure that we are accurately measuring trough drug levels)

- 9.4.3 In addition patients will have peripheral blood samples (10cc/2 teaspoons) obtained at the same intervals for:

- ADAMTS13 activity
- ADAMTS13 inhibitor assay
- ADAMTS13 antigen level

- ADAMTS13 antibody (IgG) concentration
- VWF multimeric analysis

9.5 Outpatient Visits

9.5.1 After discharge from the hospital, patients will be seen weekly in the outpatient clinic for the first month. Patients will then be seen monthly for the next 6 months, regardless of which arm of the study they were randomized to. After six months of continuous follow-up patients will then be seen every 3 months for the next 3 years to monitor the course of their disease and obtain laboratory follow-up studies (see Appendix 1)

10.0 Safety Monitoring During Study

10.0.1 To ensure the safety of all patients enrolled on this study careful monitoring and follow-up for all patients will be an important aspect of this study. At the time patients begin therapy with plasma exchange and either CSA or prednisone, all patients will be hospitalized and monitored for both response to therapy as well as any potential toxicities. Laboratory studies performed daily will monitor the clinical response to therapy, but will also monitor for the earliest signs any other end-organ toxicities (Section 9.1 – 9.4). In the CSA-treated patients the potential for renal toxicity is the primary concern, but patients on both arms will be monitored carefully for this as well as other potential toxicities through daily laboratory as well as daily clinical evaluations. After discharge, patients will continue to be monitored closely in the same manner with laboratory and clinical evaluations at regular intervals as described in Section 9.5 and Appendix 1 of the study protocol.

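### Liver enzymes are scheduled only at enrolment, although section 10.0.1 relies on the laboratory schedule to catch early end-organ toxicity in both arms

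*Combined protocol and SAP*

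**What the plan says.** - **Section 10.0.1** gives the daily laboratory studies two purposes. They follow response, and they "will also monitor for the earliest signs any other end-organ toxicities", with a pointer to sections 9.1 to 9.4. Renal toxicity is named as the main concern with CSA, but both arms are to be watched for other toxicities. The section goes on: "After discharge, patients will continue to be monitored closely in the same manner", with a pointer to section 9.5 and Appendix 1.
- **Section 9.1.1 (enrolment)** lists "liver function tests (AST, ALT, GGT, Alkaline Phosphatase", and also bilirubin.
- **Section 9.2.1 (daily during plasma exchange)** lists a blood count and a chemistry panel that ends with "BUN, Ca, and glucose) with LDH".
- **Section 9.4.2 (each follow-up visit)** lists a blood count, a chemistry panel that ends with "BUN, and glucose), total and direct bilirubin", LDH and the CSA level. Under 9.4.1, "patients will be seen weekly in the outpatient clinic for the first month", and then monthly for six months.
- **Appendix 1** has one mark in the liver function row and one in each of its two bilirubin rows on the first page, and none in those rows on the page for weeks 40 to 160.
- **Section 8.5.1** allows corticosteroid patients with an exacerbation to start CSA. "Patients treated with CSA and PE for exacerbations of TTP will then be prospectively followed as described below", which refers to sections 9.3 to 9.5.

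**The concern.** The plan takes a liver-enzyme baseline and never schedules a second measurement, so the baseline cannot show a change on study drug. The general statement in 10.0.1 suggests wider surveillance than the lists provide.

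What is at stake is safety ascertainment. Safety of CSA is a secondary objective (1.2), adverse event frequencies are to be compared between arms (14.2), and the DSMB sees the safety data at the interim analysis. An enzyme rise without symptoms would reach those tables only if a treating physician happened to order the test. In a multi-centre, open-label trial such unscheduled testing may differ by site or by arm. A fixed schedule removes that possibility.

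**Working it through.** No figure in the plan needs reproducing here. The check sets the laboratory lists side by side and counts visits.

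**1. Hepatic tests by period**

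| Period | AST, ALT, GGT, alkaline phosphatase | Bilirubin |
|---|---|---|
| Enrolment (9.1.1) | listed | listed |
| Daily during plasma exchange (9.2.1) | not listed | not listed |
| Follow-up visits (9.4.2) | not listed | total and direct |
| Appendix 1 | one mark | one mark per row |

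Sections 9.3 and 9.5 add no hepatic test. LDH is measured daily and at each visit, but the plan uses it as a response marker (8.1 requires "normalization of LDH") and does not list it among the liver function tests.

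**2. Outpatient visits on drug without a liver-enzyme test**

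- Section 9.4.1 gives 4 weekly + 6 monthly = 10 visits.
- CSA lasts six months (7.3.2). The first 4 + 5 = 9 visits reach about week 24 on the Appendix 1 time scale. CSA starts at diagnosis and visits are counted from discharge, so the ninth visit may fall just before or just after the last dose. The count is therefore 0 of about 9.
- Prednisone runs 30 days after the last exchange plus a 28-day taper (7.2.2): 30 + 28 = 58 days, or 58/7 = 8.3 weeks. That covers 4 weekly visits and 1 monthly visit, so 0 of about 5.

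**3. Inpatient window with neither enzymes nor bilirubin listed**

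- Median daily exchanges to remission in the earlier cohorts were 5 (CSA, section 3.2) and 6.5 (corticosteroids, section 2.6).
- Section 7.1.4 counts the first normal day as the first of two every-other-day exchanges, which adds 2 days: 5 + 2 = 7 and 6.5 + 2 = 8.5 days.
- Slow responders may continue for up to 4 weeks (8.2.1).

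**4. Patients who switch to CSA**

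An exacerbation falls within 30 days of stopping exchange (8.4.1). At the corticosteroid cohort's median duration, the enrolment panel is then up to 8.5 + 30 = 38.5 days old, about 5.5 weeks. It predates any CSA but also predates the prednisone course. Sections 9.3 to 9.5 schedule no repeat.

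**5. What the earlier experience rules out**

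Section 4.0 mentions creatinine rises and mild gastrointestinal toxicity in the earlier CSA cohorts (10 + 12 = 22 patients) and no hepatic event. It does not say whether enzymes were measured serially. If they were, and none of 22 rose, the one-sided 95% upper bound on the true rate is 1 − 0.05^(1/22) = 12.7%. The earlier data neither show a hepatic problem nor exclude a moderate one.

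**The case against.** The case for leaving the schedule alone has real substance.

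- **No hepatic signal.** The documents report no liver event, and 10.0.1 puts renal toxicity first. This stands and keeps the severity low. The number of missed rises is unknown and may be zero.
- **The statement in 10.0.1 is general.** It names no organ and points to lists that include the enrolment panel. It is fair to say that no specific promise of serial enzymes is broken. Still, a test done once before treatment cannot detect toxicity from that treatment.
- **Bilirubin covers most of the exposure.** A reader might infer that the liver goes unmonitored after enrolment. Section 9.4.2 does not support that: it requires total and direct bilirubin at each follow-up visit, and for responders these visits follow normalization of LDH, so direct bilirubin is usable, though less sensitive. The weakness is that a site working from Appendix 1 would not see it. That appendix is imperfect evidence, since its smear row has no mark although 9.1.1 requires a smear.
- **No dose rule would use the result.** Sections 7.3 to 7.5 adjust CSA for trough level, creatinine and clinical toxicity only. A reader might infer that patients lose a chance of timely dose adjustment. The plan as written does not support that, because an enzyme result alone would trigger no protocol action. Hence the fix must say what follows from a rise.
- **Switchers.** It is tempting to say that they start CSA with no baseline. They have the 9.1.1 panel, which is dated but not absent, and this is their first CSA course.
- **Testing during exchange.** Hemolysis and daily plasma replacement may make enzymes hard to interpret (an inference, not stated in the plan). This is a good reason not to insist on inpatient panels.

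**Conclusion.** The gap is real and narrow. After enrolment no AST, ALT, GGT or alkaline phosphatase is scheduled at any point during study drug, and no hepatic test of any kind is listed during plasma exchange. Symptomatic liver injury could still be found clinically and reported under 10.2. Only a silent rise would escape.

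A reader might go on to infer bias in the arm comparison or a threat to the trial's validity. The documents do not support either: the schedule is the same in both arms, and neither the primary endpoint nor its analysis uses liver tests. This is a cheap improvement to safety ascertainment, of low severity.

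The zero counts come directly from the lists. The visit denominators (about 9 and about 5) assume discharge close to the last exchange and the visit spacing in 9.4.1.

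**What to change.** 1. Add AST, ALT, GGT and alkaline phosphatase to 9.4.2 and Appendix 1 at the existing outpatient draws through the end of CSA (about week 24), at the same times in both arms.
2. Align the bilirubin rows in Appendix 1 with 9.4.2.
3. Repeat the panel when a corticosteroid patient starts CSA under 8.5.1, and at the visits that follow.
4. State that a clinically significant rise is reported as an adverse event under 10.2 and prompts investigator review of study drug.
5. Optional: a weekly panel during plasma exchange, read with the caution noted above.

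**Cost.** Outpatient: 9 visits × 72 patients = 648 panels, approximate. Switchers: the number is an assumption. In the earlier corticosteroid cohort 6 of 12 patients had an exacerbation; 0.5 × 36 = 18 switchers × (1 + 9) panels = 180, ignoring overlap with visits already counted. The range is 0 if none switch to 36 × 10 = 360 if all do. The optional inpatient panels would add 72 to 144 (1 to 2 per patient), with a ceiling of 4 × 72 = 288. All are assays at planned draws. No new visit, venipuncture, endpoint or sample size change is needed.
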